#### 2.4.2 Vaccination Plan

Approximately 5264 patients (~2632 vaccine recipients; ~2632 placebo recipients), 18 years of age or older will be randomized 1:1 to receive either V212 or placebo given as a 4-dose regimen approximately 30 days apart. (**Note: In India only, enrollment is restricted to patients 18 to 65 years of age.**) Each dose of V212 or placebo will be administered as a 0.5-mL subcutaneous injection preferably in the deltoid region of the arm, alternating arms for each V212 or placebo dose, if possible. Placebo will be the vaccine stabilizer for V212 with no virus antigen.

Randomization will be stratified by disease type (i.e., HM or STM) with approximately 2696 patients with STM (receiving chemotherapy) and approximately 2568 patients with HM enrolled into the study. Patients with HM will be further stratified into one of two strata, low IC or moderate to high IC (see Appendix 6.1). Randomization and stratification will be based upon a randomization schedule generated by the SPONSOR. The planned randomization schedule by vaccination group is shown in [Table 2-1](#).

Table 2-1

#### Randomization Schedule

Vaccination Group	Stratification		
	STM	HM ‡	Total
V212	1348	1284	2632
Placebo	1348	1284	2632
Total	2696	2568	5264

‡ HM population will be further stratified into one of two strata, low IC or moderate to high IC which is expected to be in 1:3 ratio approximately.

An Interactive Voice Response System (IVRS) will be used to register patient visits upon randomization and at subsequent visits. The IVRS will be used to allocate patients to vaccination group assignments during randomization according to a central randomization schedule generated by the SPONSOR. For all sites, all vaccine doses will be shipped through the IVRS.

## **2.5 LIST OF EFFICACY/IMMUNOGENICITY MEASUREMENTS**

### **2.5.1 HZ Case Determination**

[figure not shown]
The primary clinical efficacy endpoint will be the incidence of HZ. Clinical criteria for suspected HZ cases are the development of a papular or vesicular rash with a dermatomal or generalized distribution, or in the absence of a rash, clinical suspicion of VZV infection with or without the detection of VZV in diagnostic specimens from blood, CSF, lung, liver, or other organ. In immunocompromised patients, the rash of HZ may be atypical, for example involving more than one dermatome, or it may not be present. Patients who develop suspected HZ will enter 6 months of HZ follow-up.

All suspected cases of HZ will go through case adjudication in a blinded fashion by the CAC. The CAC will determine if a suspected case is a confirmed case of HZ, in their clinical opinion, and if a confirmed case make the final determination of the confirmed HZ complication(s) present. HZ case determination will be based primarily upon the results of the skin lesion PCR assay, if applicable. For those cases that do not include a skin lesion PCR assay or if the skin PCR assay is inadequate, case confirmation will be based on the result of adjudication of the clinical case description by the CAC, conducted according to the CAC SOP.

The algorithm used for determination of HZ cases is shown in [Figure 2-1](#). PCR assays for the detection of VZV DNA will be conducted as described in Section 3.3. The summary of clinical findings, laboratory and radiologic results, and results from the blood VZV PCR will be provided to the CAC.

Figure 2-1

HZ Case Determination

### **2.5.2 Secondary Efficacy Measurements**

Three secondary efficacy endpoints are defined for this protocol which will be evaluated in the STM population only and in the HM population on an exploratory basis. The first is to assess the incidence of moderate to severe HZ-associated pain [defined as 2 or more occurrences of a score 3 or greater (0-to-10 scale) in response to the prompt to rate "your pain at its worst in the last 24 hours" on the ZBPI, at any time from HZ onset through the end of the 6 month HZ-follow-up period. The second is a composite efficacy endpoint of the incidence of HZ complications, defined as the occurrence of any of the following during the study: hospitalization or prolongation of hospitalization due to HZ, disseminated HZ (including disseminated HZ rash or VZV viremia), visceral HZ, ophthalmic HZ, neurological impairment due to HZ, or administration of intravenous acyclovir therapy for treatment of HZ. The third endpoint is the incidence of PHN [defined as a worst pain score (in the last 24 hours) of 3 or greater (0-to-10 scale) in response to the prompt to rate "your pain at its worst in the last 24 hours" on the ZBPI, that persists or appears greater than or equal to 90 days after the onset of the HZ rash].

The CAC will determine whether HZ complications have occurred based on the clinical findings, laboratory and radiologic results from subjects with suspected HZ cases, as well as results from the blood VZV PCR testing.

### **2.5.3 Immunogenicity Measurements**

The study will provide an exploratory immunogenicity assessment of V212, as shown in Table 2-2. The goal is to assess the immunogenicity of the vaccine and to attempt to demonstrate correlation of immune responses to the vaccine with clinical efficacy. Serum VZV antibody levels will be measured by gpELISA in patients in the STM study group. Serum samples will be collected on Day 1/Visit 1 (prior to Dose 1) and Visit 5 (~28 days Postdose 4) based on the original enrollment plan (~2696 patients).

A subset of the study population will be enrolled in an ELISPOT substudy to measure T cell response by IFN- $\gamma$  ELISPOT. Peripheral blood mononuclear cells (PBMC) will be collected from those enrolled in the ELISPOT substudy (n ~ 1000), on Day 1/Visit 1 (prior to Dose 1) and Visit 5 (~28 days Postdose 4). Participation in the ELISPOT substudy will be limited to select sites based upon accessibility to PBMC processing laboratories. At these sites, the first 500 patients enrolled in the STM group and the first 500 enrolled in the HM group will be enrolled in the ELISPOT substudy.

Patients enrolled in the ELISPOT substudy will have a separate allocation schedule to assure a well-balanced randomization ratio. All investigative sites participating in the ELISPOT substudy will enroll each consented patient into the ELISPOT substudy until the target enrollment of 1000 patients has been met.

Table 2-2

Exploratory Immunogenicity Assessment of V212

Assay	Goal	Population
gpELISA	Assess T cell-dependent antibody response	

• STM = ~2696 patients

• HM = none

IFN- $\gamma$ ELISPOT	Assess T cell response	

• STM = ~500 patients*

• HM = ~500 patients*

\* Limited to select sites with adequate laboratory processing capabilities

## 2.6 LIST OF SAFETY MEASUREMENTS

The safety evaluation will focus on the clinical safety and tolerability profile following all 4 vaccine doses. In addition, SAE will be collected for the entire duration of the study regardless of causality.

All subjects will receive a VRC at each vaccination visit (Visits 1 through 4). On the VRC, patients will be asked to record daily oral temperature measurement, local and systemic adverse experiences, as well as concomitant medications, and non-study vaccinations. In addition, patients will be actively prompted to record on the VRC, injection-site adverse experiences for 5 days following each vaccination dose, exposure to varicella or HZ, and development of varicella/varicella-like or HZ/HZ-like rash. Patients will receive a new VRC for each dose of vaccine/placebo. The VRC will be used by the patients to collect safety information between each vaccination period (minimum 20 days postvaccination dose 1 through 3, through 28 days postvaccination dose 4). The VRC will be reviewed by study site personnel at the end of the minimum 20-day follow-up period following each V212 or placebo dose.

SAE will be collected as follows. Patients will be instructed to call the site immediately, at any time during the study, if they experience a clinical adverse experience that results in a hospitalization, prolongs a hospitalization, is a cancer or an overdose, or is another severe, unexpected, life-threatening event that could potentially be considered serious (see section 3.4.6 for a complete definition of a SAE). An SAE that is a worsening of a pre-existing condition should also be reported. Patients will also be asked, either at a scheduled study visit (Visit 1 through 5) or, after Visit 5, by telephone Periodic Safety Contact (approximately every 3 months, starting approximately 3 months following Visit 5), whether they developed a clinical adverse experience that met SAE criteria since the last contact with site personnel. Using a pre-specified script (developed by the SPONSOR) that enables the collection of relevant information related to an SAE, site personnel will query the patient and record the patient's responses to facilitate reporting of the event.

As described in Section 3.4.1.3, toxicity grading will be applied for all serious and non-SAEs in this study based on a toxicity grading scale. This is in addition to the grading of adverse experiences by maximum intensity described in Table 3-1.

Pregnancy information will be collected as described in Section 3.4.4.

## 2.7 STATISTICAL ANALYSIS PLAN SUMMARY

Key elements of the statistical analysis plan are summarized below; the comprehensive plan is provided in Section 3.5 of protocol details.

### 2.7.1 Efficacy

The primary efficacy endpoint is the incidence of HZ in the vaccine and placebo groups in the STM population, defined as the number of HZ cases per 1000 person-years of follow-up from study enrollment to the end of study. Vaccine efficacy for HZ ( $VE_{HZ}$ ) is defined as the relative reduction of the hazard rate of HZ in the V212 group compared with that in the placebo group. The primary statistical hypothesis for the primary efficacy is  $H_0: VE_{HZ} \leq 25\%$  versus  $H_1: VE_{HZ} > 25\%$ .

Appropriate multiplicity adjustment will be made for the planned interim analyses. The primary analysis will be based on a modified intent-to-treat (MITT) population, defined as all randomized patients who received at least one dose of the vaccination. The hypothesis test and corresponding CI will be based on a Cox proportional hazards regression model stratified by age (< 50 years of age versus  $\geq 50$  years of age).

Three secondary efficacy endpoints are defined for STM population. The three secondary efficacy endpoints are defined as follows: (1) incidence of moderate to severe HZ-associated pain (defined as 2 or more occurrences of a score of 3 or greater (0-to-10 scale) in response to the prompt to rate "your pain at its worst in the last 24 hours" on the ZBPI), at any time from HZ onset through the end of the 6 month HZ-follow-up period. (2) composite efficacy endpoint of the incidence of HZ complications during the study, defined as the occurrence of any of the following during the study: hospitalization or prolongation of hospitalization due to HZ, disseminated HZ (including disseminated HZ rash or VZV viremia), visceral HZ, ophthalmic HZ, neurological impairment due to HZ, or administration of intravenous acyclovir therapy for treatment of HZ. (3) the incidence of PHN (defined as a worst pain score [in the last 24 hours] of 3 or greater [0-to-10 scale] in response to the prompt to rate "your pain at its worst in the last 24 hours" on the ZBPI that persists or appears greater than or equal to 90 days after the onset of the HZ rash). A Cox proportional hazards regression model will be fitted for each of these three secondary endpoints stratified by age (< 50 years of age versus  $\geq 50$  years of age).

Additional supportive and exploratory efficacy analyses including safety and tolerability assessment and the impact of V212 on the development of HZ in the HM population, and the vaccine efficacy durability, other HZ-associated complications, the severity and duration of HZ-related pain and the interference on activities of daily living (ADL tool), Quality of Life (EuroQoL/EQ5D tool) and healthcare utilization (HCU tool) will also be provided for the HM and STM populations separately.

### **2.7.2 Immunogenicity**

All immunogenicity analyses in this study are exploratory. All patients in the STM study group will have serum samples collected at Day 1/Visit 1 and at Visit 5 (~28 days postvaccination dose 4) to assess a T-cell dependent antibody response by gpELISA. In addition, a subset of study patients (n ~ 1000) in both the STM and HM populations will participate in the ELISPOT substudy and undergo testing for VZV T-cell responses by IFN- $\gamma$  ELISPOT assay. The geometric mean titer (GMT) or geometric mean count (GMC) and geometric mean fold rises (GMFR) for both the gpELISA and ELISPOT will be provided by vaccination group at scheduled time points (see Section 1.7) for the HM and STM populations separately. A longitudinal regression model will be used to estimate the fold difference at these time points between the vaccination groups, while adjusting for the prevaccination titers (see Section 3.5.5.2) for the HM and STM populations separately. Other exploratory analyses will also be performed to determine whether these VZV-specific immune responses are associated with protection against HZ using Cox proportional hazards models in the combined STM and HM populations.

### **2.7.3 Safety**

Patients will be followed for safety for the duration of the study. In the event study close-out begins prior to all patients on study completing the required 1 year of follow-up from the time of the last vaccination dose, the study will continue to allow all patients to complete the required 1 year of follow-up. Safety and tolerability of V212 will be assessed by evaluation of all relevant safety parameters for the HM and STM populations separately. The primary safety endpoint of the study will be based on the incidence of SAE observed during the period up to 28 days Postdose 4 in each vaccination group for the STM population. Two-sided 95% CI on the proportion of any vaccine-related SAE will be provided for each vaccination group based on the exact binomial distribution [19]. The risk difference on SAE between the two groups and the corresponding two-sided 95% CI on the risk difference will also be provided using the stratified asymptotic methods proposed by Miettinen and Nurminen [20].

Other key safety evaluations will include summaries of the proportions of patients reporting the following adverse experiences: 1) systemic adverse experiences prompted for on the VRC, including varicella-like rash and HZ-like rash, occurring from Day 1 to Day 28 after any study vaccination, 2) injection-site complaints prompted for on the VRC, such as redness, swelling, and pain/tenderness/soreness occurring Day 1 through Day 5 after any vaccination, 3) elevated temperature ( $\geq 100.4^{\circ}\text{F}$  [ $\geq 38.0^{\circ}\text{C}$ ] oral or oral equivalent), from Day 1 to Day 28 after any study vaccination. The risk differences between the two vaccination groups, corresponding two-sided 95% CI on the risk difference, and the p-value for the test of significant risk difference will be provided using an asymptotic method for differences of 2 independent binomial proportions adjusting for stratification factors.

The rate of SAEs, vaccine-related SAEs and death that occur throughout the entire study follow-up period will also be summarized per 1000 person-years of follow-up by vaccination group. Additional safety summaries including SAEs, vaccine-related SAEs and death will be provided in each vaccination group for the HM and STM populations separately.

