#### Initial Evaluation of a Suspected Case of HZ *With* HZ or HZ-like Rash

At the initial evaluation of a suspected case of HZ with HZ or HZ-like rash, the following procedure should be followed:

- a) Perform a full physical examination and report relevant clinical findings. These findings include the dermatome(s) involved, morphologic characteristics of the rash, (including number and type of lesions and extent of rash), and any signs of HZ-associated complications such as disseminated HZ, secondary infections, and hospitalizations and/or mortality related to HZ. At the time of the initial rash assessment, varicella or HZ exposure history should also be obtained. Collect and record all medications administered for HZ treatment or HZ symptom relief.
- b) If rash is present, perform rash assessment to monitor for rash evolution
- c) If skin lesions are present, collect 2 swabs from the skin lesions to send for analysis by PCR as described below. PCR testing is required to confirm the presence of the virus in the lesion as well as to differentiate vaccine-strain from wild-type VZV.

**NOTE:** If both vesicles and pustules are present, vesicles are the preferred source for specimens. Follow the procedures on lesion sample collection/storage and shipping provided in the Laboratory/Procedures or Administrative Binder.

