### 3.3.2 PCR Assay for Lesion Samples

Lesion samples should be obtained from all patients presenting with a rash associated with varicella or HZ or varicella-like/HZ-like rash at the first evaluation for suspected HZ. If both vesicles and pustules are present, vesicles are the preferred source for specimens. Samples should be collected using the kit supplied by the SPONSOR, and stored immediately at  $-20^{\circ}\text{C}$  until shipment. Detailed procedures on lesion sample collection/storage and shipping are provided in the Laboratory Manual.

The purpose of the VZV PCR assay is to detect VZV and herpes simplex virus (HSV) deoxyribonucleic acid (DNA) in specimens obtained from subjects suspected of having varicella or HZ. This is the primary assay used by the central laboratory. The assay is a real-time PCR assay that uses virus-specific primers and probes to detect and discriminate among wild-type/Oka-parent VZV (VZV-WT/VZV-P), Oka-type attenuated VZV (VZV-O), and HSV DNA (HSV types 1 and 2). Virus-specific amplification is multiplexed with  $\beta$ -globin-specific primers and VIC-labeled fluorescent probe to demonstrate the presence of amplifiable host cell DNA in the clinical specimen [46].

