### **3.5.3.3 Safety**

The minimum safety follow-up period is at least 1 year following the last study vaccination.

The primary safety endpoint of the study will be based on the incidence of SAEs observed during the period up to 28 days Postdose 4 in each vaccination group. Key safety measures for an overall assessment include proportions of patients with (1) any adverse experience, (2) any injection-site adverse experience, (3) any systemic adverse experience, (4) any SAE, (5) any vaccine-related SAE, and (6) any discontinuation due to an adverse experience. Other key safety parameters include proportions of patients reporting the following adverse experiences:

1. SAEs observed Vaccination Day 1 through 28 days Postdose 4.
2. VRC-prompted systemic adverse experiences (including non-injection site varicella-like rash or HZ-like rash) following any vaccination of V212 or placebo through 28 days Postdose 4.
3. VRC-prompted injection site adverse experiences (such as redness, swelling, and pain/tenderness/soreness) Day 1 to Day 5 following any vaccination of V212 or placebo.
4. Elevated temperature ( $\geq 100.4^{\circ}\text{F}$  [ $\geq 38.0^{\circ}\text{C}$ ] oral or oral equivalent) following any vaccination of V212 or placebo through 28 days Postdose 4.
5. Any other systemic and injection-site adverse experiences not prompted for on the VRC following any vaccination with V212 or placebo through 28 days Postdose 4.
6. SAEs observed at any time for the duration of the study.

For other adverse experiences not prompted for on VRC, the safety parameters include the incidences of injection-site adverse experiences or systemic adverse experiences after any study vaccination through 28 days Postdose 4 occurring in at least 1% of the patients in either vaccination group.

Incidence of varicella/varicella-like or an HZ/HZ-like rash occurring during the period up to 28 days Postdose 4 will be summarized by skin lesion type (wild type versus vaccine strain) determined by PCR. The rate of SAEs, vaccine-related SAEs and death during the whole period of the study will be summarized per 1000 person-years of follow-up.

The safety analyses will be evaluated for the HM and STM populations separately

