For Tier-1 adverse experiences, risk differences between the two groups, corresponding two-sided 95% CI on the risk difference, and the p-value for the test of significant risk difference will be provided. The corresponding p-value will be based on the normal approximation for testing two independent binomial proportions at the two-sided 0.05 level adjusting for stratification factors. The risk difference and 95% CI will be calculated using the methods proposed by Miettinen and Nurminen [20]. Tier 1 adverse experiences include (1) systemic adverse experiences prompted for on the VRC, including varicella/varicella-like or an HZ/HZ-like rash occurring after any study vaccination through 28 days Postdose 4, (2) injection-site complaints prompted for on the VRC, such as redness, swelling, and pain/tenderness/soreness occurring Day 1 through Day 5 after any vaccination, and (3) elevated temperature ( $\geq 100.4^{\circ}\text{F}$  [ $\geq 38.0^{\circ}\text{C}$ ]), after any study vaccination through 28 days Postdose 4.

Additional summaries on Tier-1 safety parameters will also be provided by the dosing period..

For Tier-2 adverse experiences, risk differences between the two groups and the corresponding two-sided 95% CI on the risk difference will be provided using the methods proposed by Miettinen and Nurminen. This Tier-2 approach will be applied to the proportions of any other injection-site adverse experiences or systemic adverse experiences after any study vaccination through 28 days Postdose 4 that are not prompted for on the VRC but occurred in at least 1% of the patients in either treatment group.

Additional summaries on Tier-2 safety parameters will also be provided by the dosing period, and gender in each vaccination group.

Tier 3 adverse experiences will include summaries for any other adverse experiences after any study vaccination through 28 days Postdose 4.

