The rate of SAEs, vaccine-related SAEs and death that occur throughout the entire study follow-up period will also be summarized per 1000 person-years of follow-up by vaccination group, to account for potential differential follow-up time by vaccination group. The probability of mortality will also be estimated and displayed by the Kaplan-Meier curve for each vaccination group. Risk difference and the corresponding 95% CI of these long-term safety parameters between the vaccine group and placebo group will be provided using an asymptotic method for differences of 2 independent Poisson rates. Mortality and SAEs, including vaccine-related SAEs will also be listed by patient with more detailed information.

SAEs and Tier-1 adverse experiences during the primary safety follow-up period will be summarized by body system.

Summaries of varicella/varicella-like or an HZ/HZ-like rash occurring during the primary safety period, through 28 days postvaccination 4, will be provided by vaccination group and by lesion type (wild type versus vaccine strain) determined by PCR. Occurrence of opportunistic infections during the primary safety period (from Day 1 to Day 28 Postdose 4) will also be summarized as adverse experiences. Occurrence of opportunistic infections and recurrence of disease that are SAEs at any time during the study will also be summarized.

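### The tested Tier-1 rash comparison includes confirmed herpes zoster, the event V212 is meant to prevent, so a null or favourable difference does not show that the vaccine causes no rash.

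*Combined protocol and SAP*

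**What the plan says.** The operative text is in section 3.5.5.3. Tier-1 adverse experiences receive a risk difference, a 95% CI and a p-value, tested "at the two-sided 0.05 level adjusting for stratification factors". The first Tier-1 group is "systemic adverse experiences prompted for on the VRC, including varicella/varicella-like or an HZ/HZ-like rash occurring after any study vaccination through 28 days Postdose 4". Section 2.7.3 lists the same kind of item, "systemic adverse experiences prompted for on the VRC, including varicella-like rash and HZ-like rash", with the same statistics, though without the word Tier-1. Neither section restricts the rash by PCR result or by adjudication outcome.

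HZ is the subject of the primary hypothesis (section 2.1.2), and the primary efficacy analysis counts it from enrollment (section 3.5.5.1.1). An HZ rash between Dose 1 and 28 days after Dose 4 therefore counts in both the efficacy test and the tested safety item.

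The plan also has a strain split. Section 3.5.3.3 says that the incidence of these rashes "will be summarized by skin lesion type (wild type versus vaccine strain) determined by PCR". Section 3.5.5.3 says that summaries "will be provided by vaccination group and by lesion type (wild type versus vaccine strain) determined by PCR". No risk difference, CI or test is attached to that split.

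The data for a finer split are collected. Under section 3.3.2, "Lesion samples should be obtained from all patients presenting with a rash associated with varicella or HZ or varicella-like/HZ-like rash". The initial-evaluation procedure in section 3.2.17.3 gives one purpose of the PCR as to "differentiate vaccine-strain from wild-type VZV". Section 3.3.2 lists the reportable results as wild-type VZV, Oka-type VZV, HSV or negative. Under section 3.3.1.2 a VZV-negative lesion rules HZ out. Where the lesion sample is missing or inadequate, or there was no rash, the Clinical Adjudication Committee (CAC) decides.

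**The concern.** Safety in solid tumor patients is a primary objective, and rash is one of the few items given a formal between-group test. That item adds two quantities that V212 may move in opposite directions: HZ, which should fall, and any rash the vaccine causes, which would rise. The tested difference is their sum. A result near zero fits a vaccine that causes no rash and prevents little HZ in the dosing period. It also fits a vaccine that causes some rash and prevents a similar number of HZ cases.

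The strain tables only partly resolve this. They name wild type and vaccine strain. A zoster-like rash that is VZV-negative is not HZ by the plan's own rule, yet the only tested comparison pools it with HZ, and the described split does not set it apart.

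**Working it through.** **Inputs**
- 1348 patients per arm; two-sided 0.05 (sections 3.5.7.2 and 3.5.5.3).
- Placebo HZ rate 17 per 1000, taken here as person-years; VE 65% (section 3.5.7.1).
- Dose interval 20 to 40 days, about 30 (section 3.2.1). The window from Dose 1 to 28 days after Dose 4 is 3 × 30 + 28 = 118 days, with a range of 3 × 20 + 28 = 88 to 3 × 40 + 28 = 148.
- Assumed, because the documents give no such figures: other rash at 0.5% in both arms, and a vaccine-caused excess of 1.1 points.

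**Plan's own figure.** I used the pooled-variance normal approximation:

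power = Φ{ [ (p1 − p2) − 1.96·√(2p̄(1 − p̄)/n) ] / √[ (p1(1 − p1) + p2(1 − p2))/n ] }, where p̄ is the mean of p1 and p2.

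This gives 79.5% to 79.9% for all eight rows of Table 3-4, so the table's roughly 80% reproduces. The first row is 0.5% versus 1.59%.

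**Expected HZ in a 118-day window**
- Placebo: 0.017 × 118/365 = 0.55%, and × 1348 = 7.4 patients.
- V212, VE 65% from Dose 1: 0.55% × 0.35 = 0.19%, or 2.6 patients. Offset 7.4 − 2.6 = 4.8 patients, or 0.36 points.
- V212, VE 65% only after Dose 4: 0.017 × (90 + 28 × 0.35)/365 = 0.46%, or 6.3 patients. Offset 1348 × 0.017 × 28/365 × 0.65 = 1.1 patients. This does not depend on dose spacing, because only the last 28 days contribute.

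**Power to detect the 1.1-point excess on 0.5% other rash, 118 days**

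| Item tested | V212 | Placebo | Power |
|---|---|---|---|
| HZ excluded | 1.60% | 0.50% | 80% |
| HZ included, VE 0 | 2.15% | 1.05% | 62% |
| HZ included, VE 65% after Dose 4 only | 2.06% | 1.05% | 57% |
| HZ included, VE 65% from Dose 1 | 1.79% | 1.05% | 37% |

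Of the 43 points lost in the last row, 80 − 62 = 18 come from adding HZ as background events in both arms. The other 62 − 37 = 25 come from efficacy. If efficacy starts after Dose 4, its share is 62 − 57 = 5 points.

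With 1% other rash and the same 1.1-point excess, power is 64% with HZ excluded and 29% with HZ included at VE 65% from Dose 1.

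**Where the offset equals the excess.** At VE 65% from Dose 1, a vaccine-caused excess of about 0.36 points (about 5 patients) gives a net difference of about zero. A larger excess is diluted and not removed.

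**The case against.** The strongest objection is to the efficacy assumption. At 30-day spacing, 90 of the 118 days fall before Dose 4. The transplant evidence in section 3.1.2.2 reports no efficacy from a single dose and no effect of three doses on HZ incidence. Those patients may not represent solid tumor patients, but full efficacy from Dose 1 is an upper-end case. This stands, and it is why the offset is given as about 1 to about 5 patients.

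Second, vaccine-strain rash is already reported by group. Placebo contains no virus antigen, so a vaccine-strain rash on V212 would stand out as a count without a test. This also stands. The remaining gap is a between-group estimate free of HZ, and the VZV-negative rashes.

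Third, the text does not say whether varicella-like and HZ-like rash are pooled. If they are compared separately, the varicella-like item is largely unaffected. The HZ-like item is then more heavily made up of the efficacy event.

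Fourth, the primary safety endpoint is serious adverse experiences, Tier-1 p-values are unadjusted with a stated caution (section 3.5.6), and the hypothesised excess has no source. V212 is inactivated to below 0.1 PFU per dose (section 1.3). All of this limits the consequence. It does not make the mixed comparison interpretable.

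A reader might infer that prevented HZ generally cancels vaccine-caused rash, or that the plan hides a safety signal. The documents support neither. Cancellation needs an excess near the offset, and the strain tables keep vaccine-strain rash visible.

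**Conclusion.** The point holds as a limited defect in one safety comparison. The tested rash item includes the efficacy event, so its null or favourable result is not evidence that V212 causes no rash, and no planned between-group estimate supplies that evidence.

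The bias is about 1 to 5 patients per 1348, depending on when efficacy begins. Some of the power loss is added background events and would occur with an ineffective vaccine. These figures assume a constant HZ rate of 17 per 1000 person-years, a 118-day window, no dropout within it, and every HZ case appearing as a rash counted in the item. The background and excess rates are hypothetical. The 80% figure also assumes that PCR and adjudication remove HZ completely. A clean estimate is nearly free, so the change is worth making, but this is not a hidden safety failure.

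**What to change.** In sections 2.7.3 and 3.5.5.3, add a Tier-1 risk difference, 95% CI and p-value for varicella-like/HZ-like rash that excludes:
- rashes PCR-positive for wild-type VZV; and
- CAC-confirmed HZ without an adequate lesion PCR.

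The item then covers vaccine-strain rash, VZV-negative rash, and untyped rash not confirmed as HZ. The second exclusion matters: if all untyped rashes stayed in, adjudicated HZ would re-enter the comparison.

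Show the excluded HZ on its own line by group, and keep the all-rash comparison as supportive. State whether varicella-like and HZ-like rash are compared as one item or two.

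The cost is protocol wording and one or two table rows, with no new data. The downside is that the item depends on PCR and adjudication results, so misclassified or missing samples will affect it.
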